4.6 Adverse events and serious adverse events

4.6.1 Definition of adverse event (AE)

An adverse medical event that occurs in a patient or clinical trial subject after receiving the intervention, which does not necessarily have a causal relationship with the treatment. From the time the patient signs the informed consent form and is enrolled in the trial until the end of the trial, any adverse medical event occurring during this period, regardless of its causal relationship with the study intervention, shall be determined as an adverse event.

4.6.2 Definition of serious adverse event (SAE)

Events occurring during the clinical trial that result in hospitalization, prolongation of hospital stay, disability, impairment of working capacity, life-threatening conditions, death, or congenital malformations.

4.6.3 Classification of adverse events

4.6.3.1 Severity of events

Assessment and grading shall be conducted according to the definitions of the NCI-CTCAE version 4.0, divided into Grades 1–5 (please refer to NCI-CTCAE v4.0 for specific grading criteria).

4.6.3.2 Relationship to study intervention

The possible association between the AE and the investigational drug or medical device shall be assessed using a five-level classification:

- Definitely related
- Probably related
- Possibly related
- Possibly unrelated
- Unrelated

The first three levels are considered related to the investigational drug or medical device. When calculating the incidence of adverse reactions, the number of related cases (sum of the first three levels) is used as the numerator, and the total number of subjects included in the safety analysis is used as the denominator.

Table 5 Criteria for Determining the Relationship Between Adverse Events and Treatment

Criteria	Definitely related	Probably related	Possibly related	Possibly unrelated	Definitely unrelated
Reasonable temporal relationship	Yes	Yes	Yes	Yes	No
Known reaction type of the drug or device	Yes	Yes	Yes	No	No
Improvement after withdrawal of cause	Yes	Yes	Yes/No	Yes/No	No
Recurrence after re-administration or reuse	Yes	No	No	No	No
Alternative explanation possible	No	No	No	Yes	Yes

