Acupuncture, a widely practiced complementary therapy, involves stimulating specific acupoints to influence physiological processes. Over the past decade, influential clinical and preclinical research on acupuncture has expanded [7–9]. Experimental studies suggest that acupuncture may modulate multiple neurotransmitter systems—including acetylcholine, serotonin, and glutamate—thereby supporting cognitive function [10]. An adjunctive therapy that acts via a different neurotransmitter system to cholinesterase inhibitors may offer enhanced cognitive benefits. Moreover, acupoints commonly used for dementia, such as PC6 and ST36, are associated with anti-nausea and antidiarrheal effects [11–14], which may counteract side effects of cholinesterase inhibitors. Meta-analyses indicate that combining acupuncture with donepezil, the most widely used AD drug in China, may improve outcomes compared with donepezil alone[15]. Yet, existing trials are limited by short observation periods and small sample sizes, but more critically by inadequate blinding, which leaves major uncertainty about whether the observed benefits of acupuncture are genuine or primarily placebo-driven. Preclinical studies further suggest that acupuncture may influence AD pathology directly by modulating A β metabolism and tau phosphorylation [10], raising the possibility of disease-modifying effects. To date, however, little is known about whether any benefits persist after treatment cessation, a critical marker of disease modification [16].

In recent years, a plethora of studies have indicated the development of AD can be linked to gut microbiota that naturally reside in the body based on the following results: (1) Microbiome profiling of both AD patients [17,18] and mouse models [19,20] for AD has suggested alterations in the gut microbiota; (2) Modulations of the gut microbiota through germ-free rearing, dietary alterations, antibiotic treatment or fecal microbiota transplantation alter learning and memory-related behaviors [21–23]. Further, acupuncture was reported to treat diseases such as abdominal obesity,

irritable bowel syndrome by gut-brain axis. A recent study demonstrated that the acupuncture at Baihui (GV20), Yintang (GV29), and Zusanli (ST36) benignly modulated gut microbiota dysbiosis and improved cognitive function in AD mouse model [24]. Collectively, it is suggestive that gut microbiome-brain axis may be a potential mechanism of acupuncture for AD.

2 Objectives

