- 1) To evaluate if adding acupuncture to donepezil improves outcomes in patients with mild AD;
- 2) If there is an effect of acupuncture, whether the previous effect of acupuncture treatment is present after washout;
- 3) If acupuncture has a long-term effect on AD, is it related to changes in gut microbiota?

3 Study design

This is a prospective, randomized, participant-masked, sham-controlled trial, with each eligible participant randomly assigned to either active or sham acupuncture added to donepezil treatment. All participants or their legal representatives will provide written informed consent and be treated in accordance with the tenets of the Declaration of Helsinki (version 2013).

Table 1 Trial summary

Title	An efficacy and safety trial of acupuncture as adjunct to donepezil in patients with mild AD
Clinical indication	Treatment of mild AD
Trial type	Interventional
Type of control	Sham/Placebo
Route of intervention	needle stimulation + oral
Trial blinding	Single-blind
Treatment groups	Active acupuncture for 14 weeks
	Sham acupuncture for 14 weeks
Concomitant therapy	Donepezil 5 mg QD for 28 weeks
Number of trial subjects	160 in total
Estimated duration of trial	The sponsor estimates that the trial will require approximately 2.5 years from the time the first participant signs the informed consent until the last participant's last visit.
Duration of participation	Each participant will participate in the trial for approximately 30 weeks from the time the participant signs the Informed Consent Form through the final contact. After a screening phase, each subject will receive assigned treatment for 28 weeks. After the end of treatment each participant will be followed for at least 14 days.
Randomization ratio	1:1

4 Methodology

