4.1 Participant recruitment

The study will take place in the Outpatient Department, Shanghai Research Institute of Acupuncture and Meridian, Shanghai, China. The recruitment will be announced via our official account on social media and forwarded once a month. Placement of brochures and study posters in Yueyang Hospital of Integrated Traditional Chinese and Western Medicine, Shanghai University of Traditional Chinese Medicine and Ruijin Hospital, Shanghai Jiaotong University School of Medicine (collaborating hospitals) and community centers will be used to assist recruitment. In addition, we conducted disease-related science lectures in the elderly community and put up posters in the community to further promote the recruitment. Participants or their representatives will be instructed to read the informed consent and those who showed interest in the study will be scheduled for the screening visit. After presenting written informed consent, participants will be examined, and if all entry criteria are met, will commence a 4-week run-in period of treatment with donepezil hydrochloride (5 mg/capsule, China) 5 mg daily (prior AD treatments will be terminated by then). To further avoid potential confounding effects on the clinical outcomes and gut microbiota, participants will be instructed to maintain their regular diet and activity level, and refrain from probiotics, prebiotics, or synbiotics use. Upon successful completion of the 4-week run-in, participants will be scheduled to complete baseline assessments and undergo randomization. The study flowchart and proposed trial schedule are shown in Figure 1 and Table 1, respectively.

[figure not shown]

Figure 1 Flow diagram of the study protocol

Table 2 Study schedule

Visit No.	V1	V2	V3	V4	V5	V6
End of Week Relative to Study Treatment Start	-4	0	7	14	21	28
Tolerance Interval for Visit (d)	0	0	±3	±3	±7	±7
Entry and Administrative						
Eligibility	X	X				
Informed consent	X					
Physical/neurological examination	X					X
Demographics	X					
Medical history	X					
Randomization		X				
Interventions						
Active/Sham acupuncture						
Donepezil						
Outcomes Measures						
ADAS-cog12		X	X	X	X	X
MMSE		X	X	X	X	X
ADCS-ADL		X	X	X	X	X
NPI		X	X	X	X	X
Fecal samples collection		X		X		X
Additional Assessment						
Adverse events						
Treatment compliance						

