The safety of the acupuncture intervention is evaluated by documenting any symptoms possibly related to acupuncture at each acupuncture visit, which includes subcutaneous hematoma, local errhysis at acupoints, sharp pain, palpitation, nausea, dizziness and faint during acupuncture. All adverse events will be carefully documented throughout the study period. For each Data and Safety Monitoring Board

(DSMB) report, a list and summary of the reported adverse events will be presented in a blinded fashion, unless otherwise formally requested.

After the 14-week acupuncture intervention, monthly phone calls will be made to maximize retention and loss to follow up. Participants may withdraw from the study for any reason at any time. Their assessment data up to the timepoint that they withdrew will be used and such patients will not be replaced.

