6.5 Harms

An adverse medical event that occurs in a patient or clinical trial subject after receiving the intervention, which does not necessarily have a causal relationship with the treatment. From the time the patient signs the informed consent form and is enrolled in the trial until the end of the trial, any adverse medical event occurring during this period, regardless of its causal relationship with the study intervention, shall be determined as an adverse event.

Assessment and grading shall be conducted according to the definitions of the NCI-CTCAE version 4.0, divided into Grades 1–5 (please refer to NCI-CTCAE v4.0 for specific grading criteria). The possible association between the AE and the investigational drug or medical device shall be assessed using a five-level classification. The expectedness is assessed based on previously observed adverse events. If the nature, severity, or frequency of an AE does not match the risk information described in previous studies of the intervention, it shall be considered unexpected.

Once an AE occurs, details including the time of occurrence, management process, duration, and outcome shall be recorded in the case report form (CRF). For adverse events of moderate severity or above, the principal investigator, department head, and ethics committee shall be notified within 24 hours. For SAE, regardless of the cause, the investigator shall provide appropriate and timely medical treatment for the subject. This responsibility shall be explicitly stated in the study protocol and reaffirmed during investigator training. A SAE Report Form shall be completed and promptly submitted to the regulatory authorities, while simultaneously informing all participating sites and notifying the study sponsor.

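### The one defined adverse reaction incidence does not separate acupuncture/sham from donepezil, so it is not specific to acupuncture and can dilute or offset a difference between arms

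*Protocol*

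**What the plan says.** **Rating.** SAP 6.5 says: "The possible association between the AE and the investigational drug or medical device shall be assessed using a five-level classification". Protocol 4.6.3.2 uses the same wording and, after listing the grades, adds: "The first three levels are considered related to the investigational drug or medical device". Its Table 5 follows suit, with one row asking whether the event is a known reaction type of the drug or device taken together.

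**Incidence.** For the adverse reaction rate in Protocol 4.6.3.2, "the number of related cases (sum of the first three levels) is used as the numerator". Everyone in the safety analysis forms the denominator. The rule does not split by treatment component or by arm. Neither document defines the safety analysis set.

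**Exposure.** Protocol Table 1 lists donepezil as concomitant therapy for all participants: "Donepezil 5 mg QD for 28 weeks". Protocol 4.1 adds that eligible participants "will commence a 4-week run-in period of treatment with donepezil hydrochloride", and randomization comes after it. Acupuncture or sham lasts 14 weeks. Protocol 4.6.1 and SAP 6.5 collect events from consent.

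**Session record.** Protocol 4.5 evaluates acupuncture safety by recording, at each acupuncture visit, symptoms possibly related to it: "subcutaneous hematoma, local errhysis at acupoints, sharp pain, palpitation, nausea, dizziness and faint during acupuncture".

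**Expected direction.** The protocol's background says that acupoints such as PC6 and ST36 "are associated with anti-nausea and antidiarrheal effects [11–14], which may counteract side effects of cholinesterase inhibitors". It names those side effects as nausea, vomiting and diarrhea.

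**The concern.** The trial summary in Protocol Table 1 calls this an efficacy and safety trial of acupuncture. Acupuncture is the randomized component; donepezil is common to both arms. The safety contrast of interest is therefore active against sham acupuncture. The only adverse reaction rate that the documents define is pooled over drug and device.

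Pooling matters here for three reasons:
- Donepezil reactions occur in both arms. They enter the numerator as background that has nothing to do with the randomized comparison, and reactions in the run-in can enter before anyone has had acupuncture.
- Nausea is on both lists: it is a session symptom under Protocol 4.5 and a cholinesterase inhibitor effect in the background.
- The background gives a reason why the two kinds of reaction might move in opposite directions. Penetrating needles with current could produce more local reactions than a blunt, non-penetrating sham, while acupuncture might reduce cholinergic effects. A single figure nets one against the other.

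At stake is a safety statement that adverse reactions were similar between arms when the acupuncture component was not similar.

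**Working it through.** **Step 1. What the wording allows.** The documents state no expected adverse reaction rate, so there is no figure of theirs to reproduce. The text can be read in two ways.

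*Reading A: drug or device covers both treatments.* A donepezil reaction and an acupuncture reaction both count as related, and both enter one numerator. A donepezil reaction in the run-in also fits, since collection starts at consent. (The opening sentence of Protocol 4.6.1 refers to events after receiving the intervention, but the next sentence and 4.6.4 start at consent.)

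*Reading B: investigational means acupuncture alone.* Donepezil reactions then have no attribution. Donepezil also becomes a possible alternative explanation. In Table 5 that row is No in all three related columns and Yes only in the two unrelated ones. Nausea during a session in a participant on donepezil can then be graded possibly unrelated and leave the numerator.

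Under A the rate is not specific to acupuncture. Under B it can miss acupuncture events that overlap with donepezil's.

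**Step 2. Illustration of reading A.** Only the arm size, 80 (Protocol 4.8), and the two-sided 5% level (Protocol 4.9) come from the documents. All reaction rates are assumptions.

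Let a be the acupuncture reaction rate in an arm and d the donepezil reaction rate. With independence, the proportion with any related reaction is 1 − (1 − a)(1 − d). Power uses the normal approximation: Φ[(Δ − 1.96·SE0)/SE1], where SE0 uses the average of the two proportions and SE1 uses each arm's own.

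*Separate rating, a = 15% active, 2% sham.* Δ = 13.0 points; SE0 = √(2 × 0.085 × 0.915/80) = 0.0441; SE1 = √((0.15 × 0.85 + 0.02 × 0.98)/80) = 0.0429; (0.130 − 0.0864)/0.0429 = 1.02; power 85%.

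*Pooled, d equal in both arms:*

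| d | Active | Sham | Difference (points) | Power |
|---|---|---|---|---|
| 10% | 23.5% | 11.8% | 11.7 | 49% |
| 20% | 32.0% | 21.6% | 10.4 | 32% |
| 30% | 40.5% | 31.4% | 9.1 | 22% |
| 40% | 49.0% | 41.2% | 7.8 | 17% |

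For the 30% row: 1 − 0.85 × 0.70 = 0.405 and 1 − 0.98 × 0.70 = 0.314.

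*Pooled, d = 30% sham but lower in active, as the background suggests:*
- d = 22.5% active: 1 − 0.85 × 0.775 = 34.1%, against 31.4%: +2.7 points.
- d = 15% active: 1 − 0.85 × 0.85 = 27.75%, against 31.4%: −3.65 points. The excess reverses.

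*Smaller acupuncture effect, a = 10% against 2%:* power is 57% rated separately, and 24% down to 9% pooled as an equal d rises from 10% to 40%.

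**Step 3. Sensitivity to the overlap assumption.** Suppose instead that the two kinds of reaction never fall on the same participant, with d = 20% in both arms and a = 10% against 2%. The pooled rates are 30% and 22%. The difference stays at 8 points, while the ratio falls from 10/2 = 5.0 to 30/22 = 1.36. Precision still suffers: SE0 rises from 0.0375 to 0.0694, and power falls from 57% to 21%. So shrinkage of the risk difference depends on overlap; the loss of power does not.

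**The case against.** A reader might infer that acupuncture's own toxicity cannot be obtained from this trial. The documents do not support that. Protocol 4.5 sets up an acupuncture-specific symptom record at every session, documents all adverse events as well, and 4.6.5 puts the details of each on the case report form. This objection stands. What it leaves open is reporting: the session record is not linked to the incidence in 4.6.3.2, SAP 6.5 does not mention it, and it lists nausea without distinguishing donepezil as a cause.

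Randomization also does much of the work. Both arms take donepezil, so a by-arm comparison of hematoma, nausea or diarrhea reflects active against sham acupuncture without any causality rating. This too stands. It follows that the trial is not barred from examining whether acupuncture eases donepezil's side effects, although that is a background suggestion and neither an objective nor an endpoint. But neither document plans such a comparison.

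Nor should one say that everyone is needled. Sham is blunt, non-penetrating and without current.

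That each event is rated only once is the natural reading, not an explicit statement. The section title refers to the study intervention and donepezil is labelled concomitant, so reading B is arguable. It avoids the pooled numerator but brings the Table 5 problem instead.

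Finally, the reaction rates are invented. Rates can be chosen that cancel exactly: with no overlap, 20% + 2% in sham and 12% + 10% in active both give 22%. That shows that cancellation is possible, not that it is likely. Participants also enter only after completing the run-in, so nothing in the documents supports any particular donepezil rate after randomization.

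**Conclusion.** The point holds as a gap in how harms are attributed and reported. The adverse reaction incidence in Protocol 4.6.3.2 is either pooled over two treatments or, on the narrower reading, liable to lose overlapping events. On neither reading is it a clean acupuncture rate.

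The size is unknown because the documents give no reaction rates. Under the assumed 15% against 2%, an equal donepezil background of 10% to 40% cuts power from 85% to between 49% and 17%. A fall in donepezil reactions in the active arm can remove or reverse the pooled difference. These figures rest on 80 per arm, independence between the two kinds of reaction, and a by-arm comparison that the plan does not itself describe.

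The point does not show that acupuncture harm goes unrecorded, and it does not touch the primary or secondary efficacy analyses. It is a cheap improvement worth making.

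**What to change.** In Protocol 4.6.3.2 and SAP 6.5:
1. Rate relatedness separately for each event, once to acupuncture/sham and once to donepezil, and apply Table 5 to each in turn. State that the other study treatment does not by itself count as an alternative explanation; otherwise nausea could be graded unrelated on both ratings.
2. Report each by arm as the number of participants with at least one related event, for events after randomization. List run-in events separately.
3. Define the safety analysis set that supplies the denominator.
4. Tabulate the Protocol 4.5 session symptoms by arm.
5. Keep the combined incidence as an additional line if wanted.

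The cost is one extra case report form field, one extra table and the matching text. Events already recorded could be re-attributed from their descriptions by masked staff, provided this is done before unblinding and needle-site details are withheld. Active sites are on the head, limbs and abdomen and sham sites are lumbar and calf, so the site of a bruise can reveal the arm. Withholding the site makes some attributions less certain, which is a real limit on doing this retrospectively.

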In 2019, Alzheimer’s Disease International estimated that there were over 50 million people living with dementia globally, a figure set to increase to 152 million by 2050 [1]. Alzheimer’s disease (AD) is the most common type of dementia in older people, characterized by early accumulation of amyloid beta (A β) in the brain, which triggers tau pathology, synaptic loss, and neuronal death. These processes ultimately lead to cognitive decline and dementia. Recent advances have produced disease-modifying therapies such as aducanumab [2], lecanemab[3], and donanemab [4], which promote amyloid clearance and may provide clinical benefit. However, their long-term safety remains uncertain, and their high cost limits accessibility, particularly in countries such as China. For most patients, treatment remains focused on symptomatic therapy with two classes of FDA-approved drugs: cholinesterase inhibitors (donepezil, rivastigmine, galantamine) for mild to moderate AD, and the N-methyl-D-aspartate–receptor antagonist memantine for moderate to severe disease. Higher doses of cholinesterase inhibitors may improve symptoms in advanced stages but are often poorly tolerated due to cholinergic side effects, including nausea, vomiting, and diarrhea [5,6]. There remains a pressing need for both safer symptomatic options and affordable disease-modifying strategies.

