4.6.3.3 Expectedness

Expected adverse reactions are collected in a standardized format. The expectedness is assessed based on previously observed adverse events. If the nature, severity, or frequency of an AE does not match the risk information described in previous studies of the intervention, it shall be considered unexpected.

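### Table 5 counts an adverse event as related only if it is a known reaction with no possible alternative explanation, and leaves other plausible patterns without any category

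*Protocol*

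**What the plan says.** Protocol section 4.6.3.2 sets five causality levels and states: "The first three levels are considered related to the investigational drug or medical device". For adverse-reaction incidence, "the number of related cases (sum of the first three levels) is used as the numerator". The denominator is everyone in the safety analysis.

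Table 5 gives the criteria for each level. Two rows matter most:

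- "Known reaction type of the drug or device" is Yes for all three related columns and No for both unrelated columns.
- "Alternative explanation possible" is No for all three related columns and Yes for both unrelated columns.

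Section 4.6.3.3 treats expectedness separately. If the nature, severity or frequency of an event departs from earlier risk information, "it shall be considered unexpected".

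SAP section 6.5 repeats the five-level classification without criteria, so it neither replaces nor relaxes Table 5. It also specifies no adverse-event table by arm. The related-event incidence is the only adverse-event rate in either document with a stated numerator and denominator.

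**The concern.** A level called 'Possibly related' would normally hold events for which the intervention is one candidate cause among others. Here it excludes them, because it demands that no alternative be possible. It differs from 'Probably related' only in accepting either answer on improvement after withdrawal. An event of a new type cannot be counted either, even when nothing else explains it, although section 4.6.3.3 foresees events whose nature is new.

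Section 4.5 lists symptoms to be sought at each acupuncture visit, among them "sharp pain, palpitation, nausea, dizziness and faint during acupuncture". In people with dementia who all take donepezil, a rater may well see the drug or the disease as a possible explanation for nausea or dizziness. Such an event is then a known reaction with a possible alternative, and Table 5 has no column for it.

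At stake is the related-event incidence, in a trial whose title names safety beside efficacy.

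**Working it through.** **Inputs.** The five criteria and five columns of Table 5, protocol section 4.6.3.2. Every row has all five entries, so nothing suggests that text was lost in extraction. Write T = reasonable timing, K = known reaction type, I = improvement after withdrawal, R = recurrence on reuse, A = alternative explanation possible.

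| Level | T | K | I | R | A | Counted |
|---|---|---|---|---|---|---|
| Definitely related | Y | Y | Y | Y | N | yes |
| Probably related | Y | Y | Y | N | N | yes |
| Possibly related | Y | Y | Y/N | N | N | yes |
| Possibly unrelated | Y | N | Y/N | N | Y | no |
| Definitely unrelated | N | N | N | N | Y | no |

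The plan states no figure to reproduce here, so the check is an enumeration.

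**Step 1: all patterns.** Five yes/no criteria give 2^5 = 32 patterns. Each is matched to every column, with Y/N accepting either answer.

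- Patterns reaching a counted level: YYYYN, YYYNN and YYNNN, so 3 of 32.
- Patterns in 'Possibly unrelated': YNYNY and YNNNY, so 2.
- Patterns in 'Definitely unrelated': NNNNY, so 1.
- Patterns fitting no column: 32 − (3 + 2 + 1) = 26.
- YYYNN fits both 'Probably' and 'Possibly related'.
- None of the 16 patterns with K = N, and none of the 16 with A = Y, reaches a counted level.

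**Step 2: plausible timing only (T = Y, 16 patterns).**

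| K | A | Patterns | Counted | Possibly unrelated | No column |
|---|---|---|---|---|---|
| Y | N | 4 | 3 | 0 | 1 |
| Y | Y | 4 | 0 | 0 | 4 |
| N | N | 4 | 0 | 0 | 4 |
| N | Y | 4 | 0 | 2 | 2 |
| Total | | 16 | 3 | 2 | 11 |

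The other 26 − 11 = 15 unclassified patterns have no plausible timing and would hardly be called related anyway. The 11 are the ones that matter.

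**Step 3: the corrected levels.** Under the definitions given in the fix, the 16 patterns with T = N are 'Unrelated'. Among the 16 with T = Y, 1 is 'Definitely related' and 1 is 'Probably related'. Two (K = N, A = Y, R = N, either answer on I) are 'Possibly unrelated'. The remaining 16 − 1 − 1 − 2 = 12 each have at least one of K = Y, A = N or R = Y and are 'Possibly related'. The sum is 16 + 1 + 1 + 2 + 12 = 32, with no pattern in two levels. Counted patterns go from 3 to 14.

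These are counts of patterns, not of events. Patterns are not equally common, so 3 and 14 say nothing about the rates themselves.

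**The case against.** The strongest reply is that Table 5 is incomplete rather than biased, and that little depends on it. Much of this stands.

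- **Nausea.** A reader might infer that nausea can never count, because all participants take donepezil. The documents do not support that. The background section links "cholinergic side effects, including nausea, vomiting, and diarrhea" to higher doses of cholinesterase inhibitors. Participants complete a four-week donepezil run-in before randomization, and a rater could find no alternative for nausea that begins during a session. Section 4.6.3.2 also does not say whether donepezil is the assessed drug or an outside explanation. Nausea is an example of the problem, not a class always excluded.
- **Direction.** A reader might infer that unclassified events are pushed into 'Possibly unrelated'. No text says so. Without recurrence, a known reaction with an alternative misses 'Possibly related' on one row and 'Possibly unrelated' on one row. So does a new type without an alternative. Raters could go either way.
- **Unexpected events.** Only new types are shut out. An event of a known type that is unexpected in severity or frequency can still count.
- **Reach.** All adverse events are recorded whatever their cause (sections 4.5 and 4.6.1). The safety board receives a list and summary with no stated relatedness filter. Events of moderate severity or above are notified within 24 hours regardless of cause (section 4.6.5). Efficacy is unaffected, and the same table applies to both arms.

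What does not stand is that this makes the table usable. A rule that gives no answer for 11 of 16 plausibly timed patterns, and two answers for another, does not define the numerator it feeds.

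**Conclusion.** The defect is real and concerns the classification rule and the related-event incidence, not the capture of adverse events. Applied literally, the table keeps two kinds of plausibly timed event out of the numerator: known reactions with a possible alternative, and new types of reaction without one. Applied loosely, it leaves the numerator to each rater's discretion.

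A reader might infer a downward bias of known size. The documents give no adverse-event rates and no rule for events that fit no column, so the size cannot be computed. An undercount is certain only under literal use, and only if such events occur.

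The conclusion assumes that Table 5 is the operative criterion, since neither document gives another, and that each criterion is answered yes or no. It does not depend on whether donepezil counts as the assessed drug. That ambiguity is a further reason to separate the two attributions.

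**What to change.** Replace the criteria in Table 5 so that every event has exactly one level:

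- **Definitely related** and **Probably related**: unchanged.
- **Possibly related**: plausible timing, no higher level met, and at least one of known reaction type, no alternative explanation, or recurrence on reuse.
- **Possibly unrelated**: plausible timing, new type, an alternative explanation, and no recurrence.
- **Unrelated**: no plausible timing. Use one label for this level, since the list says 'Unrelated' and the table 'Definitely unrelated'.

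Simply entering Yes/No for known type and alternative explanation under 'Possibly related' would not work. Every 'Possibly unrelated' pattern would then also meet 'Possibly related', and the edge of the numerator would be lost.

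Record relation to acupuncture and relation to donepezil as two separate judgements. Have raters blinded to arm re-code the events already recorded. Carry the criteria into SAP section 6.5, and report all-cause adverse events by arm alongside the related-event incidence. The all-cause table needs no new data and does not depend on causality grading.

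The cost is a table edit, one more case report form item and some re-coding. The reported related-event rate may rise; by how much cannot be said from the documents.
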